10.0 STUDY PROCEDURES

10.1 Visit 1 – Screening/Randomization

After obtaining written informed consent and Health Insurance Portability and Accountability Act (HIPAA) authorization, site staff will perform/assess the following in the order suggested below.

1. Each screened subject should be assigned a subject identifying number, based on the next available number in the eCRF.
2. Collect subject demographic information.
3. Collect ocular and non-ocular medical history.
4. Collect concomitant medications taken during the previous 12 months. Ask specifically about the use of Iluvien during the previous 36 months.
5. Administer UPT for female subjects of child-bearing potential.
6. Conduct in-office HbA1c test following test manufacturer guidelines.
7. Conduct the following ocular assessments on both eyes (refer to [Section 15.0](#) for further details):

- a. BCVA by ETDRS
- b. Slit-lamp Biomicroscopy
- c. IOP by Tonopen or Applanation
- d. Spectral Domain OCT
- e. Indirect Ophthalmoscopy/Dilated Fundus Examination
- f. Fundus Photography
- g. Fluorescein Angiography
8. Assess inclusion/exclusion criteria.
9. If subject is eligible, randomize the subject by entering information into the IWRS.
10. Dispense kit number provided by IWRS and provide dosing instructions/diary to the subject.
11. The first dose of study medication should be administered within the clinic under site staff supervision, and subsequent doses will be self-administered following the subject's visit.
12. Assess for any AEs occurring from the time of informed consent.
13. Provide instruction for the subject to:
 - a. Dose IP as instructed
 - b. Complete dosing information in subject diary.
 - c. Return for Visit 2 (Day 14) in 2 weeks (\pm 2 days).
14. Prepare and upload OCT images to the central reading center, and upload fundus photography to ShareFile.

Note: Subjects can be re-screened at the discretion of the Investigator if there is reasonable clinical evidence to suggest the subject may qualify after initial screen failure. The Investigator should contact the Sponsor to discuss re-screenings prior to conducting the visits.

10.2 Visit 2 (Day 14)

This visit will occur on Day 14 \pm 2 days as calculated from Visit 1 (Day 0), and the following evaluations will be performed:

1. Collect and record any AEs occurring since the last visit.
2. Collect and record any new or changed concomitant medications since the last visit.
3. Conduct the following ocular assessments on both eyes (refer to [Section 15.0](#) for further details):
 - a. BCVA by ETDRS
 - b. Slit-lamp Biomicroscopy
 - c. IOP by Tonopen or Applanation
 - d. Spectral Domain OCT
 - e. Indirect Ophthalmoscopy/Dilated Fundus Examination

- f. Fundus Photography
4. Collect used IP kit/dosing diary and conduct drug accountability. Ensure that any dosing noncompliance is addressed with the subject.
5. Dispense kit number provided by IWRS and provide dosing instructions/diary to the subject.
6. Provide instruction for the subject to:
 - a. Dose IP as instructed.
 - b. Complete dosing information in subject diary.
 - c. Return for Visit 3 (Day 28) in 2 weeks (\pm 2 days).
7. Prepare and upload OCT images to the central reading center, and upload fundus photography to ShareFile.

10.3 Visit 3 (Day 28)

This visit will occur on Day 28 \pm 2 days as calculated from Visit 1 (Day 0), and the following evaluations will be performed:

1. Collect and record any AEs occurring since the last visit.
2. Collect and record any new or changed concomitant medications since the last visit.
3. Conduct the following ocular assessments on both eyes (refer to [Section 15.0](#) for further details):
 - a. BCVA by ETDRS
 - b. Slit-lamp Biomicroscopy
 - c. IOP by Tonopen or Applanation
 - d. Spectral Domain OCT
 - e. Indirect Ophthalmoscopy/Dilated Fundus Examination
 - f. Fundus Photography
 - g. Fluorescein Angiography
4. Collect used IP kit/dosing diary and conduct drug accountability.
5. Provide instruction for the subject to:
 - a. Return for Visit 4 (Day 42) in 2 weeks (\pm 2 days).
6. Prepare and upload OCT images to the central reading center, and upload fundus photography to ShareFile.

10.4 Visit 4 (Day 42)

This visit will occur on Day 42 \pm 2 days as calculated from Visit 1 (Day 0), and the following evaluations will be performed:

1. Collect and record any AEs occurring since the last visit.

2. Collect and record any new or changed concomitant medications since the last visit.
3. Conduct the following ocular assessments on both eyes (refer to [Section 15.0](#) for further details):
 - a. BCVA by ETDRS
 - b. Slit-lamp Biomicroscopy
 - c. IOP by Tonopen or Applanation
 - d. Spectral Domain OCT
 - e. Indirect Ophthalmoscopy/Dilated Fundus Examination
 - f. Fundus Photography
4. Provide instruction for the subject to:
 - a. Return for Visit 5 (Day 56) in 2 weeks (\pm 2 days).
5. Prepare and upload OCT images to the central reading center, and upload fundus photography to ShareFile.

10.5 Visit 5 (Day 56) or Early Termination Visit

This visit will occur on Day 56 \pm 2 days as calculated from Visit 1 (Day 0), or on the date of early termination, if applicable. The following evaluations will be performed:

1. Collect and record any AEs occurring since the last visit.
2. Collect and record any new or changed concomitant medications since the last visit.
3. Administer UPT to females of child-bearing potential.
4. Conduct the following ocular assessments on both eyes (refer to [Section 15.0](#) for further details):
 - a. BCVA by ETDRS
 - b. Slit-lamp Biomicroscopy
 - c. IOP by Tonopen or Applanation
 - d. Spectral Domain OCT
 - e. Indirect Ophthalmoscopy/Dilated Fundus Examination
 - f. Fundus Photography
5. Prepare and upload OCT images to the central reading center, and upload fundus photography to ShareFile.

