	
potential study subject is examined. The primary efficacy outcome is determined by the OCT assessments from the reading center.
 
Study subjects will administer the randomly assigned treatment for 28 days. There is an additional 28-day post-treatment follow-up period. All study subjects will return for examination every 2 weeks for 8 weeks (2 months).
 
Clinical assessments will include slit-lamp examination, intraocular pressure (IOP) measurement, BCVA, OCT, fluorescein angiography (FA), and fundus photography. Adverse events (AEs) will be recorded at all study visits.
 
Rescue therapy with a VEGF inhibitor can be administered to any study subject who experiences a significant decrease in BCVA, defined as BCVA loss of >7 letters from baseline (Visit 1 – Screening/Randomization), accompanied by an increase in OCT central subfield thickness of >75μm as compared to the previous study visit, as assessed by the Investigator.
 
Potential study participants will be asked to sign an informed consent document prior to screening. Once it is determined that all eligibility criteria have been met, subjects will be randomized to 1 of the 2 treatment arms. All study subjects and site staff will be masked to the treatment assignment.
 
The safety and exploratory efficacy of SF0166 will be evaluated over the course of the study. Since this is Phase I/II clinical study, no formal hypotheses testing is planned; descriptive statistics will be used to summarize the study outcomes.

Treatments:	
• SF0166 2.5% low dose BID• SF0166 5.0% high dose BID
Subject Selection:	
Inclusion Criteria:
 
1. Male or female, 18 years of age or older.2. Retinal thickening secondary to type 1 or type 2 diabetes mellitus with DME defined as central subfield thickness \geq325 μm on spectral domain OCT in the study eye.3. BCVA between 78 and 25 letters, inclusive, in the study eye at the screening/randomization visit using ETDRS testing, with BCVA decrement primarily attributable to DME.4. Treatment naïve (i.e., no previous anti-VEGF treatment in the study eye) or previously treated study eye with adequate washout defined below:
a. Lucentis (ranibizumab): 30-day washout

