2.0 OVERVIEW OF STUDY PLAN

Visit Number	1	2	3	4	5	Unscheduled
Visit Window	0 days	14 ± 2 days (2 weeks)	28 ± 2 days (4 weeks)	42 ± 2 days (6 weeks)	56 ± 2 days (8 weeks) or Early Termination	N/A
Procedure/Assessment						
Informed Consent	X					
Demographics	X					
Medical/Ocular History	X					
Concomitant Medications	X	X	X	X	X	X
Urine Pregnancy Test (UPT) ¹	X				X	(x)
HbA1c Test	X					
BCVA (ETDRS) ²	X	X	X	X	X	(x)
Slit Lamp Biomicroscopy ²	X	X	X	X	X	(x)
IOP by Tonopen or Applanation ²	X	X	X	X	X	(x)
Spectral Domain OCT ²	X	X	X	X	X	(x)
Indirect Ophthalmoscopy/Dilated Fundus Examination ²	X	X	X	X	X	(x)
Fundus Photography ²	X	X	X	X	X	(x)
Fluorescein Angiography ²	X		X			(x)
Inclusion/Exclusion	X					
Adverse events	X ³	X	X	X	X	X
Dispense IP	X	X				(x)
Dispense instructions/diary	X	X				(x)
Collect IP and dosing diary		X	X			(x)
(x) = as needed ¹ = Required for females of childbearing potential (i.e., who are not postmenopausal for at least 1 year or surgically sterile for at least 6 weeks from Visit 1 – Screening/Randomization) ² = Performed on both eyes ³ = collected from the time of informed consent						

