8.0 SUBJECT POPULATION

The study population includes approximately 40 subjects, 18 years of age or older, randomized at approximately 10 sites. The goal is to enroll 40 subjects, 20 in each study arm, allowing for a minimum of 30 subjects to complete the study. To participate in the study, the subject must have center-involved diabetic macular edema (i.e., retinal thickening secondary to type 1 or type 2 diabetes mellitus with DME and central subfield thickness ≥ 325 μm on spectral domain OCT) in the study eye, either be treatment naïve or have been previously treated in the study eye with an adequate washout period (see [Sections 1.0](#) and [9.3](#)), achieve BCVA between 78 and 25 letters, inclusive, in the study eye using ETDRS testing, with BCVA decrement primarily attributable to DME, be willing able to attend all study visits and adhere to study regimen, and be willing to give written informed consent.

The duration of study participation is 8 weeks (± 2 days); including an on-treatment period of 28 days, and a post-treatment follow-up period of 28 days.

The complete inclusion and exclusion criteria are presented in [Section 1.0](#).

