11.4 Discontinued Subjects

Discontinued subjects will not be replaced. If a subject requires discontinuation of IP and placement on rescue therapy, that subject should be continued in the study and followed through the end of the study.

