12.0 SAFETY

12.1 Safety Outcomes

The safety parameters for the study include:

- BCVA
- Slit-lamp findings
- Fundus findings
- IOP
- AEs

The Investigator may choose to discontinue a subject at any time, if in his/her opinion, it is in the best interest of the subject's safety.

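### A subject discontinued for safety without rescue has no planned off-drug assessment after the Early Termination visit, whereas completers and rescued subjects are followed to Day 56

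*Combined protocol and SAP*

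**What the plan says.** All references are to the combined protocol and SAP.

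- **Planned follow-up.** The Synopsis (Section 1.0) states: "There is an additional 28-day post-treatment follow-up period". Section 8.0 describes participation as "including an on-treatment period of 28 days, and a post-treatment follow-up period of 28 days". Visits 4 and 5 (Days 42 and 56) fall in the second period.
- **Early termination.** The last scheduled column in Section 2.0 is headed "56 ± 2 days (8 weeks) or Early Termination"; only the as-needed unscheduled column comes after it. Section 10.5 places the Visit 5 procedures at Day 56 "or on the date of early termination, if applicable". No later scheduled contact is described.
- **Rescued subjects.** Section 11.4 says of a subject who stops IP and is placed on rescue "that subject should be continued in the study and followed through the end of the study". Section 10.7 says the same. Both tie retention to rescue.
- **Safety discontinuation.** Section 12.1: "The Investigator may choose to discontinue a subject at any time", where this serves the subject's safety. No follow-up rule is attached, and the text does not say whether the subject stops IP, leaves the study, or both.
- **General provisions.** Section 10.6 permits unscheduled visits, with ocular assessments optional. Section 12.7 makes the Investigator responsible for follow-up after the study and for passing on new safety information, including changes to reported adverse events.
- **IP and diary.** The row "Collect IP and dosing diary" in Section 2.0 is marked at Visits 2 and 3, and as needed at unscheduled visits. It is not marked in the Visit 5/Early Termination column, and Section 10.5 has no such step.

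**The concern.** Safety comes first in the trial's objective, and the safety parameters in Section 12.1 are mostly examination findings: BCVA, slit-lamp, fundus and IOP. Whether a change in one of these resolves, persists or worsens once the drug is stopped can be learned only from an examination made after stopping. The 28-day follow-up supplies two such examinations to completers, and the rescue provision supplies them to rescued subjects. A subject discontinued because of a suspected ocular effect is the one in whom the off-drug course is of most interest, yet the plan schedules no off-drug examination for that subject.

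Three things are at stake:

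- data on whether the event resolved off drug;
- adverse events that arise after termination;
- the Day 42 and Day 56 summaries of IOP, BCVA and OCT, which would lack these subjects.

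Section 11.3.4 summarizes adverse events as numbers and percentages of subjects, with no stated allowance for unequal observation time. If stopping were more frequent at one dose, the arms would be compared over different lengths of follow-up.

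**Working it through.** **1. Reproduce the plan's own figure.** Visit 3 is at Day 28 ± 2 and Visit 5 at Day 56 ± 2 (Section 2.0). Post-treatment period = 56 − 28 = 28 days, which agrees with Sections 1.0 and 8.0. With the windows, the shortest span is 54 − 30 = 24 days and the longest is 58 − 26 = 32 days.

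**2. Planned off-drug observation by type of subject.**

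| Subject | Planned off-drug observation | Source |
|---|---|---|
| Completer | 28 days (24 to 32), two visits | 1.0, 2.0, 8.0 |
| Stops IP and starts rescue | From IP stop to Day 56; 28 days or more if the stop is by Day 28 | 10.7, 11.4 |
| Terminated on the last dosing day, no rescue | 0 days | 2.0, 10.5, 12.1 |
| Terminated on Day 42 after finishing treatment | 42 − 28 = 14 days | 2.0, 10.5 |

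The zero therefore belongs to termination during treatment, when the last dose and the termination visit coincide.

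**3. What remaining on the schedule would supply.** For a stop on day *t*, the off-drug observation to Day 56 is 56 − *t*, and the remaining visits are those of Days 14, 28, 42 and 56 that fall after *t*.

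| Stop day | Days to Day 56 | Remaining scheduled visits |
|---|---|---|
| 7 | 49 | 4 |
| 14 | 42 | 3 |
| 21 | 35 | 3 |
| 28 | 28 | 2 |

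**4. Size across the trial.** The documents give no rate of safety withdrawal. Section 8.0 plans 40 subjects and allows for at least 30 completers, so 40 − 30 = 10 non-completers for any reason. Planned post-treatment subject-days (Day 28 to Day 56) = 40 × 28 = 1,120. If *k* subjects terminate on treatment, *k* × 28 of these are lost. Taking *k* from 1 to 10 as an assumption:

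- *k* = 1: 28 / 1,120 = 2.5%
- *k* = 2: 56 / 1,120 = 5.0%
- *k* = 5: 140 / 1,120 = 12.5%
- *k* = 10: 280 / 1,120 = 25%

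**5. Which analyses are affected.** The safety set is all randomized subjects (Section 11.1), and adverse events are collected from consent and again at the termination visit (Sections 2.0, 10.5, 12.5). The event that led to withdrawal therefore enters the summaries. The Per Protocol set requires both periods to be completed as planned, so these subjects would probably be outside it even with further visits. The gain from continued assessment falls mainly on the safety set and the modified ITT set.

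**The case against.** The strongest reply is that the protocol does not abandon these subjects. Section 12.7 requires the Investigator to maintain follow-up and to give the sponsor new safety information, and Section 10.6 allows an unscheduled visit at any time with every ocular assessment available. This stands in part. A reader might infer that there is no follow-up at all, and the documents do not support that. However, neither section sets a date, a duration or a required ocular assessment, so what is collected will depend on the site.

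Four other strong readings are tempting and should not be made:

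- **Adverse event percentages describe only subjects who tolerated the drug.** They do not, for the reason in step 5 of the working. Only events arising after termination could be missed. The selection concern applies to the later-visit summaries.
- **Every stop of IP without rescue must end in study exit.** No section says so. Such a subject is told neither to leave nor to stay. The sections do not contradict one another; one case is left unspecified, and sites may handle it differently.
- **Exposure is unknown in subjects who terminate early.** Section 9.4 requires collection records and return of all IP. Section 9.5 requires comparison with the subject's daily dosing record and entry of missed doses at each clinic visit. What is missing is a line in the termination visit's list of procedures.
- **A quarter of follow-up will be lost, or half in one arm (10 of 20).** The 10 non-completers are a planning allowance for any cause, including withdrawn consent and loss to follow-up, which this change cannot recover. The 25% needs all 10 to terminate during treatment without rescue, and the 50% also needs all of them in one arm. Both are upper bounds.

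**Conclusion.** The point holds for planned assessment. Continued assessment after stopping IP is provided only when rescue is started. For a safety discontinuation without rescue, the termination visit is the only one the plan provides for, and the text does not distinguish stopping the drug from leaving the study. Planned off-drug observation is 0 days for a subject terminated on the last dosing day, against 28 days (24 to 32) for a completer.

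Across the trial the loss is 2.5% to 25% of planned post-treatment subject-days. This rests on an assumed 1 to 10 on-treatment terminations in 40 subjects, and the true number may lie anywhere in that range or be zero. The missing IP and diary step is a minor inconsistency with Sections 9.4 and 9.5. The change is worth making because it is cheap and yields off-drug safety and outcome data that the plan would otherwise not schedule.

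**What to change.** 1. Reconcile Sections 10.5, 10.7, 11.4, 12.1 and 12.7 by defining stopping IP and leaving the study as separate events, recorded separately.
2. Apply the data-collection sentence already in Sections 10.7 and 11.4 to subjects who stop IP without rescue: remaining scheduled assessments through Day 56 unless consent is withdrawn. Keep the Early Termination visit for subjects who leave the study.
3. Add IP and diary collection to Section 10.5 and to the Visit 5/Early Termination column of Section 2.0 for subjects who terminate before Visit 3, in line with Sections 9.4 and 9.5.

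This concerns assessments and data only. It changes no rule on when treatment is stopped or rescue is given, and the clinical care of these subjects remains for the sponsor and the Investigator to determine. The cost is amendment wording and one table cell. The visits are already in the schedule, but some subjects who have stopped the drug would be asked to attend them.

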10.6 Unscheduled Visit(s)

Unscheduled visits may occur at any time for any reason. The following evaluations should be performed during these visits:

1. Collect and record any AEs occurring since the last visit.

2. Collect and record any new or changed concomitant medications since the last visit.

The following evaluations *may* be performed during these visits:

3. Administer UPT to females of child-bearing potential.
4. Conduct the following ocular assessments on both eyes (refer to [Section 15.0](#) for further details):
 - a. BCVA by ETDRS
 - b. Slit-lamp Biomicroscopy
 - c. IOP by Tonopen or Applanation
 - d. Spectral Domain OCT
 - e. Indirect Ophthalmoscopy/Dilated Fundus Examination
 - f. Fundus Photography
 - g. Fluorescein Angiography
5. Dispense kit number provided by IWRS and provide dosing instructions/diary to the subject.
6. Collect used IP kit/dosing diary and conduct drug accountability.
7. Provide instruction for the subject to:
 - a. Dose IP as instructed, if applicable
 - b. Complete dosing information in subject diary, if applicable
 - c. Return for next regularly scheduled visit, or follow-up unscheduled visit.
8. Prepare and upload OCT images to the central reading center, and upload fundus photography to ShareFile.

10.7 Rescue Therapy

Rescue therapy with a VEGF inhibitor can be administered to any study subject who experiences a significant decrease in BCVA, defined as BCVA loss of >7 letters from baseline (Visit 1 – Screening/Randomization), accompanied by an increase in OCT center subfield thickness of >75 μ m as compared to the previous study visit, as assessed by the Investigator. The OCT images completed during the assessment for rescue therapy initiation should also be uploaded to the central reading center.

Therapies can include:

- Avastin (bevacizumab), or
- Lucentis (ranibizumab), or
- Eylea (aflibercept), or
- Macugen (pegaptanib)

Note: Steroid and focal laser photocoagulation rescue is not permitted during the study.

Subjects who discontinue IP and are started on rescue therapy should continue with the visit schedule and assessments through the end of the study.

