9.3.2 Prohibited Treatments

Use of the following treatments is not allowed during the study and for the timeframes specified:

- Within 36 months (3 years) prior to study enrollment
 - Illuvien (fluocinolone acetonide intravitreal implant)
 - Retisert (fluocinolone acetonide intravitreal implant)
- Within 180 days (6 months) prior to study enrollment
 - Ozurdex (dexamethasone intravitreal implant)
- Within 90 days (3 months) prior to study enrollment
 - Focal laser photocoagulation or intravitreal/periocular/topical ocular steroids of any type in the study eye
 - Any intraocular surgery in the study eye
 - Any change in dose to a concomitant topical ophthalmic medication in the study eye
- Within 60 days (2 months) prior to study enrollment
 - Eylea (aflibercept) in the study eye
- Within 45 days prior to enrollment
 - Macugen (pegaptanib) in the study eye
- Within 30 days (1 month) prior to enrollment

- Lucentis (ranibizumab) in the study eye
- Avastin (bevacizumab) in the study eye
- YAG laser treatment in study eye

Subjects taking a stable dose of topical ophthalmic medications at study enrollment should be instructed not to dose study medication within 1 hour of investigational product dosing.

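### Rescue counts retinal thickening only from the previous visit, so from Day 28 an eye that thickened gradually, or lost vision one visit after thickening, does not qualify

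*Combined protocol and SAP*

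**What the plan says.** Section 10.7 permits rescue with a VEGF inhibitor for a subject who "experiences a significant decrease in BCVA, defined as BCVA loss of >7 letters from baseline", provided this comes with a CST increase of more than 75 µm "as compared to the previous study visit, as assessed by the Investigator". The synopsis states the same rule. Neither place offers a from-baseline thickness criterion or a discretionary route to rescue, and 10.7 rules out steroid and focal laser rescue.

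Section 9.3.2 says "Use of the following treatments is not allowed during the study and for the timeframes specified" and lists the anti-VEGF agents for the study eye, so rescue under 10.7 is the only way to give one to the study eye within the protocol. Section 11.4 speaks of a subject who "requires discontinuation of IP and placement on rescue therapy" but sets no criterion of its own. Both 10.7 and 11.4 want rescued subjects followed to the end of the study.

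Outside the rescue rule, Section 12.1 says "The Investigator may choose to discontinue a subject at any time" where safety calls for it, and 12.7 makes the Investigator responsible for adequate and safe medical care during the study.

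OCT and BCVA are done at all five scheduled visits (Days 0, 14, 28, 42 and 56, Section 2.0). Dosing lasts 28 days, and investigational product is collected for the last time at Visit 3.

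**The concern.** The two halves of the rule use different reference points. Letters lost accumulate from Visit 1, but the thickness comparison starts afresh at every visit. An eye can move steadily away from its baseline on both measures without ever showing a large enough thickness step between two consecutive visits. An eye can also meet each half of the rule, but at different visits.

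What is at stake is subject protection and retention. The literal text leaves such an eye without anti-VEGF treatment unless the subject leaves the study or the study ends.

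**Working it through.** **Inputs, all from the documents.** BCVA criterion: loss greater than 7 letters from Visit 1 (10.7). CST criterion: rise greater than 75 µm from the previous study visit (10.7). Scheduled visits: Days 0, 14, 28, 42 and 56, each post-baseline visit ±2 days (2.0). The plan gives no figure of its own on cumulative thickening, so there is none to reproduce.

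**Largest total rise that never meets the CST criterion.** The inequality is strict, so a step of exactly 75 µm does not count. The ceiling is 75 µm × number of intervals between scheduled visits:

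| Visit | Intervals since Visit 1 | Ceiling |
|---|---|---|
| Day 14 | 1 | 1 × 75 = 75 µm |
| Day 28 | 2 | 2 × 75 = 150 µm |
| Day 42 | 3 | 3 × 75 = 225 µm |

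At Day 14 the previous scheduled visit is Visit 1, so the two references coincide and nothing is missed. The gap opens at Day 28. These are ceilings for even steps: a step of 76 µm at any visit meets the CST criterion at that visit.

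**Example 1, gradual thickening** (illustrative values).

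| Day | CST (µm) | Step | Rise from Visit 1 | Letters lost | Rescue under 10.7? |
|---|---|---|---|---|---|
| 0 | 400 | – | – | – | – |
| 14 | 470 | +70 | +70 | 3 | No: neither part met |
| 28 | 540 | +70 | +140 | 9 | No: CST step too small |
| 42 | 610 | +70 | +210 | 12 | No: CST step too small |

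**Example 2, vision loss after the thickness jump** (illustrative values).

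| Day | CST (µm) | Step | Rise from Visit 1 | Letters lost | Rescue under 10.7? |
|---|---|---|---|---|---|
| 0 | 400 | – | – | – | – |
| 14 | 520 | +120 | +120 | 6 | No: BCVA part not met |
| 28 | 525 | +5 | +125 | 10 | No: CST step too small |

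At Day 28 the second eye is 125 µm thicker and 10 letters worse than at entry. It has met each part once, but never both at one visit.

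**How long the gap lasts.** It runs from Visit 3 to Visit 5, nominally 56 − 28 = 28 days. With the visit windows, the shortest span is 54 − 30 = 24 days and the longest 58 − 26 = 32 days. Examinations continue every 2 weeks.

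**Unscheduled visits.** Section 10.6 says "Unscheduled visits may occur at any time for any reason" and allows OCT at them. Section 10.7 does not say whether such a visit counts as the previous one. If it does, each extra OCT adds an interval and raises the ceiling by a further 75 µm. The results above do not depend on this.

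**The case against.** The strongest reply is that this is a deliberate and coherent rule, stated identically in two places. Comparing with the previous visit asks for recent, active thickening. In Example 2 the retina is nearly stable at Day 28 (+5 µm), so not triggering there is how such a rule works. Using different references for vision and thickness is not a contradiction. All of that stands, and the point is therefore a suggestion for improvement, not an error.

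The second reply is that subjects are largely protected already. A reader might infer that a deteriorating eye is denied care. The documents do not support that. At scheduled visits the gap begins when dosing is ending, so a subject discontinued under 12.1 to receive standard anti-VEGF gives up no study treatment, apart from a day or two if Visit 3 comes early. Section 12.7 places care with the Investigator, examinations are two weeks apart, and the final visit is scheduled for "56 ± 2 days (8 weeks) or Early Termination", so BCVA and OCT are still recorded on leaving. What remains is narrower. Neither 12.1 nor 12.7 makes the eye eligible for rescue, and discontinuation ends the follow-up that 10.7 and 11.4 are written to keep.

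A reader might also infer that many of the 40 subjects would be affected. The documents give no distribution of changes in CST or BCVA between visits. Any percentage would rest wholly on assumed inputs and would move with the model chosen, so none is offered.

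**Conclusion.** The gap is real on the literal text and limited in consequence. From Day 28, an eye with more than 7 letters lost can be up to 150 µm thicker than at entry (225 µm at Day 42) through steps of 75 µm or less and still not qualify. An eye whose vision loss lags its thickening by one visit does not qualify either. The ceilings assume scheduled visits only and even steps.

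The effect is on subject protection and retention for roughly the last four weeks of the study. The practical choice for such a subject is to remain without rescue or to leave follow-up. It would go too far to say that the efficacy result is biased: the documents give no basis for that, and no formal hypothesis test is planned. Severity is low. This is a cheap improvement that the sponsor could make.

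**What to change.** In Section 10.7 and the synopsis, keep the BCVA part and replace the OCT part with: *accompanied by an OCT center subfield thickness >75 µm greater than at Visit 1 – Screening/Randomization, or >75 µm greater than at the previous study visit, as assessed by the Investigator.*

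Every eye that qualifies now still qualifies, because the present condition is kept as one of the two alternatives. Both examples then qualify at Day 28 (+140 µm with 9 letters lost; +125 µm with 10 letters lost). No new measurement is needed. Rescue remains permitted, not compulsory, so an Investigator who judges that an eye is settling need not treat it.

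The cost is that a few more eyes may be rescued. At scheduled visits the new alternative adds eyes only from Day 28, so it is their Day 42 and Day 56 values that may carry an anti-VEGF effect. Summaries at those visits should flag rescued eyes.

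There is one further consequence to settle. Section 11.1 makes the Per Protocol population primary but does not say whether a rescued subject stays in it. If not, each added rescue also takes that subject's Day 14 and Day 28 values out of the primary analysis. Discontinuation under 12.1 would do the same, so the change is no worse in that respect for a subject who would otherwise have been withdrawn. A sentence in 11.1 stating how rescued subjects are classified would remove the doubt.
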